12.3 Treatments

Study treatment

The analysis of study treatment data will be based on the safety set. The number of visits with active and placebo i.v. infusions received will be presented by treatment group.

The duration of exposure to study treatment will also be summarized by treatment group. In addition, the number and percentage of subjects with cumulative exposure levels (e.g., any exposure, ≥ 4 weeks, ≥ 8 weeks, etc.) will be presented.

Prior and concomitant medication

Prior and concomitant medications will be summarized in separate tables by treatment group.

Prior medications are defined as treatments taken and stopped prior to first dose of study treatment. Any medication given at least once between the day of first dose of randomized study treatment and the date of the last study visit will be a concomitant medication, including those which were started pre-baseline and continued into the period where study treatment is administered.

Medications will be presented in alphabetical order, by Anatomical Therapeutic Classification (ATC) codes and grouped by anatomical main group. Tables will show the overall number and percentage of subjects receiving at least one treatment of a particular ATC code and at least one treatment in a particular anatomical main group.

Significant prior and concomitant non-drug therapies and procedures will be summarized by primary system organ class and MedDRA preferred term.

Prior surgeries and procedures are defined as surgeries and procedures done prior to first dose of study treatment. Any surgeries and procedures done between the day of first dose of study treatment and within the date of the last study visit will be a concomitant surgeries and procedures, including those which were started pre-baseline and continued into the period where study treatment is administered.

The number and percentage of subjects receiving prior and concomitant axSpA therapy will be presented by randomized treatment group as well as the reasons for stopping their therapies (primary lack of efficacy, secondary lack of efficacy, lack of tolerability, other) and the total duration of exposure to axSpA therapies previously. [REDACTED]

12.4 Analysis of the primary endpoint(s)

Details of the testing strategy including primary and secondary endpoints are provided in [Section 12.5.1](#).

12.4.1 Definition of primary endpoint(s)

The primary efficacy variable is response to treatment according to the ASAS40 criteria at Week 16 in patients with active axSpA (AS and nr-axSpA). The analysis of the primary variable will be based on the FAS population.

12.4.2 Statistical model, hypothesis, and method of analysis

The estimand for primary endpoint is defined as follows:

- A. Population: defined through appropriate inclusion/exclusion criteria to reflect the targeted axSpA population (AS and nr-axSpA)
- B. Variable: composite of remaining on the study and on randomized treatment through 16 weeks and achieving ASAS40 response at 16 weeks
- C. Intercurrent event: the intercurrent event is captured through the variable definition
- D. Population-level summary: difference in proportions of responders between the secukinumab and placebo arms

The statistical hypothesis for ASAS40 being tested is that there is no difference in the proportion of subjects fulfilling the ASAS40 criteria at Week 16 in the secukinumab i.v. regimen versus placebo regimen.

Let p_0 denote the proportion of ASAS40 responders at Week 16 for placebo regimen and p_1 denote the proportion of ASAS40 responders at Week 16 for secukinumab i.v. regimen.

In statistical terms, $H_1: p_1 = p_0$, $H_{A1}: p_1 \neq p_0$, i.e.,

H_1 : secukinumab i.v. regimen is not different to placebo regimen with respect to ASAS40 response at Week 16

The primary analysis will be conducted via logistic regression with treatment and stratification factor (disease condition) as factors and weight as a covariate. Difference in marginal response proportions with p-value and 95% confidence interval (CI) will be presented comparing secukinumab i.v. regimen to placebo.

12.4.3 Handling of missing values/censoring/discontinuations

Missing data for ASAS40 response and other binary efficacy variables (e.g., ASAS 5/6, etc.) for data up to Week 16 will be handled as follows:

1. Patients who drop out of the trial for any reason will be considered as non-responders from the time they drop out through Week 16
2. Patients who do not have the required data to compute responses (e.g., ASAS components) at baseline and at the specific timepoint will be classified as non-responders at the specific timepoint.

Patients who are unblinded prior to the scheduled time point will be considered non-responders from the time of unblinding up to Week 16. The primary analysis will use the non-responder imputation.

Continuous variables (e.g., ASAS components) will be analyzed using a mixed-effects model repeated measures (MMRM) which is valid under the missing at random (MAR) assumption. As such, single-point imputation of missing data will not be performed (e.g., LOCF). For analyses of these parameters, if all post-baseline values are missing then these missing values will not be imputed and this patient will be removed from the analysis of the corresponding variable, i.e., it might be that the number of patients providing data to an analysis is smaller than the number of patients in the FAS.

12.4.4 Sensitivity and Supportive analyses

Sensitivity analyses and supportive analyses will be conducted in order to provide evidence that the results seen from the primary analysis are robust. These analyses will center on the deviations in model assumptions and the treatment of missing data.

In order to determine the robustness of the logistic regression model used for the primary analysis, ASAS40 response at Week 16 will also be evaluated using a non-parametric ANCOVA model (Koch et al 1998) with the same independent variables as the logistic regression model. In addition, further logistic regression models may be conducted which explore the impact of other baseline or disease characteristics (and respective interactions with treatment group) on response.

The impact of missing data on the analysis results of ASAS40 will be assessed as well by repeating the logistic regression model using different ways to handle missing data.

These may include, but are not limited to:

- Multiple imputation
- Observed data analysis
- Tipping point analysis

12.5 Analysis of secondary endpoints

12.5.1 Efficacy and/or Pharmacodynamic endpoint(s)

The secondary efficacy variables and the method for adjusting for multiplicity are described below. Secondary efficacy variables will be analyzed using the FAS population. Handling of missing data for secondary variables included in the testing strategy will be the same as for the primary variable.

Estimand definition for the secondary variables

Estimand definition for the secondary binomial variables (e.g., ASAS 5/6, etc.) is the following:

- A. Population: defined through appropriate inclusion/exclusion criteria to reflect the targeted axSpA population
- B. Variable: composite of remaining on the study and on randomized treatment through 16 weeks and achieving variable response at 16 weeks
- C. Intercurrent event: the intercurrent event is captured through the variable definition
- D. Population-level summary: difference in proportions of responders between the treatment conditions

The estimand of binary variables is (secukinumab vs placebo) obtained from a logistic regression model at week 16 in the FAS population. In the analysis, patients dropping out or being unblinded before week 16 or having missing response data at week 16 are considered as non-responders.

Estimand definition for the secondary continuous variables (e.g., BASDAI, etc.) is the following:

- A. Population: defined through appropriate inclusion/exclusion criteria to reflect the targeted axSpA population
- B. Variable: change from baseline in the variable of interest
- C. Intercurrent event: had no intercurrent events occurred before week 16
- D. Population-level summary: difference in variable means between the treatment conditions

The estimand of continuous variables at week 16 is (secukinumab vs placebo) obtained from MMRM in the FAS population assuming patients dropping out or having missing data at week 16 are missing-at-random. MAR imputation will be implemented through an MMRM or multiple imputation model.

ASDAS-CRP major improvement at Week 16

Response at Week 16 to ASDAS-CRP major improvement criteria will be evaluated using a logistic regression model with treatment, stratification factor (disease condition) as factors and weight and baseline score as a covariate.

BASDAI at Week 16

Between-treatment differences in the change from baseline in BASDAI will be evaluated using MMRM with treatment group, stratification factor (disease condition) and analysis visit as factors and baseline BASDAI score and weight as continuous covariates. Treatment by analysis visit and baseline BASDAI score by analysis visit will be included as interaction terms in the model. An unstructured covariance structure will be assumed for the model.

ASAS 5/6 at Week 16

The proportion of patients meeting the response criteria will be evaluated using a logistic regression model with treatment group, stratification factor (disease condition) as factors and weight as a covariate.

BASFI at Week 16

Between-treatment differences in the change from baseline in BASFI will be evaluated using MMRM with treatment group, stratification factor (disease condition) and analysis visit as factors and baseline BASFI score and weight as continuous covariates. Treatment by analysis visit and baseline BASFI score by analysis visit will be included as interaction terms in the model. An unstructured covariance structure will be assumed for the model.

SF-36 PCS at Week 16

See [Section 12.5.7](#) Patient Reported Outcomes.

ASQoL at Week 16

Summary statistics of observed data by visit and change from baseline in ASQoL will be provided for each treatment regimen. Between-treatment differences will be evaluated using MMRM. Treatment group, stratification factor (disease condition) and analysis visit will be included as categorical factors and baseline ASQoL scores and weight as continuous covariates. Treatment by analysis visit and baseline ASQoL scores by analysis visit will be included as interaction terms in the model. An unstructured covariance structure will be assumed for the model.

hsCRP at Week 16

For the change in hsCRP, since evidence from the literature would suggest that the data are not normally distributed (Huffman et al 2006), analysis will be performed on the \log_e ratio of the treatment value vs baseline value (calculated by dividing the post-baseline value by the baseline value and then applying the \log_e transformation) to normalize the distribution of hsCRP at each analysis visit. Between-treatment differences in the change in hsCRP relative to baseline will be evaluated using MMRM with treatment group, stratification factor (disease condition) and analysis visit as factors and \log_e baseline hsCRP and weight as continuous covariates. Treatment by analysis visit and \log_e baseline hsCRP by analysis visit will be included as interaction terms in the model. An unstructured covariance structure will be assumed for the model. The estimate and the 2-sided 95% confidence intervals obtained from the model will be back transformed to the original scale.

ASAS20 at Week 16

The proportion of patients meeting the response criteria will be evaluated using a logistic regression model with treatment group, stratification factor (disease condition) as factors and weight as a covariate.

ASDAS-CRP inactive disease at Week 16

Response at Week 16 to ASDAS-CRP inactive disease criteria will be evaluated using a logistic regression model with treatment, stratification factor (disease condition) as factors and weight and baseline score as a covariate.

ASAS partial remission at Week 16

Response at Week 16 to ASAS partial remission criteria will be evaluated using a logistic regression model with treatment, stratification factor (disease condition) as factors and weight as a covariate.

PSQI at Week 16

Summary statistics of observed data by visit and change from baseline in total PSQI score will be provided for each treatment regimen. Between-treatment differences will be evaluated using MMRM. Treatment group, stratification factor (disease condition) and analysis visit will be included as categorical factors and baseline PSQI scores and weight as continuous covariates. Treatment by analysis visit and baseline PSQI scores by analysis visit will be included as

interaction terms in the model. An unstructured covariance structure will be assumed for the model.

Testing Strategy

The following null hypotheses will be included in the testing strategy, and type-I-error will be set such that a family-wise type-I-error of 5% is kept:

Primary objective:

H₁: secukinumab i.v. regimen is not different to placebo regimen with respect to signs and symptoms (ASAS40 response) in axSpA patients at Week 16

Secondary objectives:

H₂: secukinumab i.v. regimen is not different to placebo regimen with respect to ASDAS-CRP major improvement in axSpA patients at Week 16

H₃: secukinumab i.v. regimen is not different to placebo regimen with respect to change from baseline in total BASDAI in axSpA patients at Week 16

H₄: secukinumab i.v. regimen is not different to placebo regimen with respect to ASAS 5/6 response in axSpA patients at Week 16

H₅: secukinumab i.v. regimen is not different to placebo regimen with respect to change from baseline in BASFI in axSpA patients at Week 16

H₆: secukinumab i.v. regimen is not different to placebo regimen with respect to change from baseline in SF-36 PCS in axSpA patients at Week 16

H₇: secukinumab i.v. regimen is not different to placebo regimen with respect to change from baseline in ASQoL in axSpA patients at Week 16

H₈: secukinumab i.v. regimen is not different to placebo regimen with respect to change from baseline in hsCRP in axSpA patients at Week 16

[figure not shown]
H₉: secukinumab i.v. regimen is not different to placebo regimen with respect to ASAS20 response in axSpA patients at Week 16

H₁₀: secukinumab i.v. regimen is not different to placebo regimen with respect to ASDAS-CRP inactive disease in axSpA patients at Week 16

H₁₁: secukinumab i.v. regimen is not different to placebo regimen with respect to ASAS partial remission in axSpA patients at Week 16

H₁₂: secukinumab i.v. regimen is not different to placebo regimen with respect to change from baseline in PSQI in axSpA patients at Week 16

Figure 12-1 Testing strategy

The family-wise error will be set to $\alpha=5\%$ and it will be controlled with the proposed sequential testing strategy as described in Figure 12-1. The primary hypothesis (H_1) for the primary objective (ASAS40 at Week 16) for secukinumab i.v. regimen versus placebo will be tested at α -level. If the hypothesis H_1 is rejected then the whole α will be passed to the next hypothesis (H_2) which will be tested at α -level. This procedure will continue (pending rejection of the null hypotheses) until H_{12} is rejected.

Of note, in the description above, rejection of a hypothesis refers to rejection of the two-sided hypothesis; however the level of a rejected hypothesis is only passed on according to the sequence for the test of another hypothesis if the treatment effect is in favor of secukinumab.

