8.3.1.4 ASAS partial remission criteria

The ASAS partial remission is defined as a value not above 2 units in each of the four main domains on a scale of 10.

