12.8 Sample size calculation

12.8.1 Primary endpoint(s)

An overall type I error (2-sided) of 5% will be used to control type I error. Secukinumab i.v. regimen will be tested versus placebo with respect to the primary endpoint (ASAS40 response at Week 16). A sample size of 250 axSpA patients (200 AS patients and 50 nr-axSpA patients) per group is deemed appropriate to achieve adequate power for the primary and secondary endpoints for this study.

An ASAS40 response rate of about 28.2% for the AS population in the placebo group at week 16 was reported in a published phase III study (CAIN457F2320). The ASAS40 response to secukinumab 150 mg is estimated to be 44.9% in the AS population based on the lower bound of the 90% confidence interval of risk difference from the meta-analysis of 3 phase III studies (CAIN457F2310, CAIN457F2320 and CAIN457F2308). With 250 patients per treatment group (200 AS patients and 50 nr-axSpA patients), there would be approximately 96% power to detect a treatment difference of 16.7% in ASAS40 response rates between secukinumab and placebo in the evaluation of the primary efficacy hypothesis at Week 16 (Chi Square test, NQuery 7.0). The overall sample size will be 500 patients (400 AS patients and 100 nr-axSpA patients) for a randomization ratio of 1:1.

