12.8.2 Secondary endpoint(s)

The estimated power with the chosen sample size for secondary efficacy endpoints based on the pooled results of the same phase III studies (CAIN457F2310, CAIN457F2320 and CAIN457F2308) are summarized in [Table 12-1](#) for binary endpoints and [Table 12-2](#) for continuous endpoints.

Table 12-1 Summary of power for binary secondary endpoints

Endpoint	Response Rate		Power
	Secukinumab(N = 200 AS + 50 nr-axSpA)	Placebo (N = 200 AS + 50 nr-axSpA)	
ASAS 5/6	44.2%	19.5%	99%
ASDAS-CRP major improvement	27.8%	6.4%	99%
ASAS20	59.0%	38.4%	99%
ASDAS-CRP inactive disease	13.6%	3.5%	97%
ASAS partial remission	15.2%	5.5%	92%

Table 12-2 Summary of power for continuous endpoints

Endpoint	Mean change from baseline		Common standard deviation	Power
	Secukinumab(N = 200 AS + 50 nr-axSpA)	Placebo (N = 200 AS + 50 nr-axSpA)		
hsCRP ¹	-0.79	0.09	0.867	99%
BASDAI	-2.61	-1.48	2.241	99%
BASFI	-2.14	-1.13	2.253	99%

SF-36 PCS	6.87	3.99	6.898	99%
ASQoL	-4.46	-2.56	4.714	99%
PSQI ²	-1	0	3.9	81%

¹ hsCRP is in log scale

² Source: mean change from baseline is from [Karatas et al 2018](#) (AS study, median was used) and common standard deviation is from [Taylor-Gjevve et al 2011](#) (RA study, largest standard deviation was used).

13 Ethical considerations and administrative procedures

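### ASAS partial remission (H11) is a fixed Week 16 state but is modelled without any baseline disease score, a small loss of efficiency that one pre-named covariate would recover

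*Protocol*

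**What the plan says.** Protocol 8.3.1.4 makes partial remission an end state: it is "defined as a value not above 2 units in each of the four main domains on a scale of 10". No change from baseline enters the definition.

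Protocol 12.5.1 gives the H11 model: "Response at Week 16 to ASAS partial remission criteria will be evaluated using a logistic regression model with treatment, stratification factor" (disease condition), plus weight. No baseline score appears. In the same section the models for ASDAS-CRP major improvement (H2) and ASDAS-CRP inactive disease (H10) end with "as factors and weight and baseline score as a covariate". The other ASAS responses (ASAS40 in 12.4.2; ASAS 5/6 and ASAS20 in 12.5.1) have disease condition and weight only.

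Two other places bear on this:

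- The general by-visit model for binary variables, in the text after the PSQI paragraph of 12.5.7, allows a baseline score where suitable. It names neither partial remission nor a covariate for it.
- The Data analysis row of the protocol summary lists treatment, stratum and weight for all binary secondary endpoints.

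The summary measure is a difference in responder proportions (12.5.1). H11 is the eleventh of twelve hypotheses tested in sequence, and only PSQI (H12) follows. The SAP supplied covers the final analysis and does not restate the Week 16 models (SAP 2.6).

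**The concern.** With a fixed target, a subject who enters with domain scores near 5 has less far to go than one who enters near 8. Baseline level should therefore predict the outcome. The entry criteria (5.1) do not remove that variation. Of the four domains, only total back pain has a direct floor; patient global, BASFI and the morning-stiffness mean have none. All four are collected at baseline (Table 8-1).

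A prognostic covariate left out of a model for a marginal difference is precision left unused. H11 has the second-lowest stated power among the secondary endpoints (92%; PSQI has 81%), and a failure there also stops H12. What is at stake is a small amount of power for the last two tests, not the validity of any result.

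**Working it through.** **Inputs from the documents.** Protocol 12.8.1: "An overall type I error (2-sided) of 5% will be used to control type I error"; "A sample size of 250 axSpA patients (200 AS patients and 50 nr-axSpA patients) per group"; "for a randomization ratio of 1:1". Table 12-1 (12.8.2): "ASAS partial remission 15.2% 5.5% 92", where the last figure is the stated power in percent. Section 5 anticipates 10% drop-out before Week 16; 12.4.3 counts drop-outs as non-responders.

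**Step 1: the stated 92%.** With p1 = 0.152, p0 = 0.055, n = 250 and mean rate 0.1035:

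- SE under the null = √(2 × 0.1035 × 0.8965 / 250) = 0.02725
- SE under the alternative = √((0.152 × 0.848 + 0.055 × 0.945) / 250) = 0.02690
- z = (0.097 − 1.96 × 0.02725) / 0.02690 = 1.621, so power = 94.7%

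The stated 92% is approached in three ways:

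- Continuity correction (subtract 1/250 from the difference): 93.0%.
- 225 per arm after 10% drop-out: 92.4%.
- Both rates cut by 10% for non-response (0.1368 and 0.0495): 92.1%.

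The stated figure is sound, and the unadjusted test is already well powered.

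**Step 2: from variance reduction to power.** Multiply both SEs by √(1 − v), where v is the proportional cut in variance. The equivalent number of extra subjects per arm is 250/(1 − v) − 250.

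| v | Power | Gain (points) | Equivalent extra subjects per arm |
|---|---|---|---|
| 0 | 94.7% | – | – |
| 1% | 94.9% | 0.2 | 3 |
| 2% | 95.1% | 0.4 | 5 |
| 5% | 95.7% | 0.9 | 13 |
| 9% | 96.4% | 1.6 | 25 |
| 16.1% | 97.5% | 2.7 | 48 |

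**Step 3: how large v might be.** The documents give no baseline-to-Week-16 association, so the correlation below is an assumption. Each model calibrates the Week 16 state to 5.5% and 15.2% and compares the marginal difference with and without the mean of the four baseline domains.

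- *Model A*: four correlated 0–10 domains, with back pain at least 4 at entry. SE ratios of 0.991, 0.982, 0.971 and 0.953 for correlations 0.3, 0.4, 0.5 and 0.6 give v = 1 − ratio² = 1.8, 3.6, 5.7 and 9.2%. Extended to correlation 0.2 and with 10% drop-out as non-response, v is 1, 2, 4, 6 and 9%, and power rises by about 0.2 to 1.6 points.
- *Model B*: four standard-normal domains, within-visit correlation 0.6, stratum and weight in the model, 2,000 trials per cell.

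| Correlation | v, Model A with drop-out | v, Model B | Power without → with baseline, Model B |
|---|---|---|---|
| 0 | – | 0% | 95.9 → 95.9% |
| 0.2 | 1% | 1.6% | 95.7 → 95.8% |
| 0.3 | 2% | 3.5% | 95.6 → 95.8% |
| 0.4 | 4% | 6.3% | 95.5 → 96.3% |
| 0.5 | 6% | 10.4% | 95.4 → 97.3% |
| 0.6 | 9% | 16.1% | 95.1 → 98.3% |

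In Model B, entering all four domains separately gave almost the same v as their mean.

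**Step 4: is adjustment safe with few events?** Expected responders are 250 × 0.152 + 250 × 0.055 = 38 + 13.75, about 52. In Model B with 5.5% in both arms (about 27.5 responders), rejection at nominal 5% ranged over 4.8–5.8% without baseline, 5.2–6.1% with the single mean and 5.2–6.2% with four terms. The simulation standard error per cell is √(0.05 × 0.95 / 2000) = 0.5 points. One summary covariate is the prudent choice.

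**The case against.** The strongest reply is that nothing has been overlooked. A reader might infer that the protocol adjusts H10 for baseline because it is an end state, and then missed H11. The documents do not support that. ASDAS major improvement is a change criterion, yet its model also carries the baseline score, while every ASAS response, partial remission included, is modelled without one. The pattern follows the instrument: ASDAS is one composite with a natural baseline value, whereas the ASAS responses are multi-domain rules. This stands, so H11 should not be called inconsistent with a principle the plan states. The case for adjustment rests on the nature of the endpoint.

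It also stands that the H10 wording cannot simply be copied. Neither document defines a baseline score for partial remission, so the covariate has to be created and named.

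The gain is small and rests on an unknown correlation. At 0.2 it is negligible, and at 0.6 the two models differ nearly twofold (9% against 16%). This limits the weight of the point but does not reverse its direction: no scenario showed a loss of precision beyond simulation error.

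Finally, the by-visit model in 12.5.7 leaves room for a baseline score. It does not prescribe one for this endpoint or displace the specific H11 model in 12.5.1, so it does not settle the matter.

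**Conclusion.** The concern holds as a minor efficiency point. H11 is a fixed end state analysed without baseline disease level. Over an assumed correlation of 0.2 to 0.6, adjustment would cut the variance by about 1 to 9% (up to 16% in Model B) and add about 0 to 3 power points, most likely around 1 or less. If baseline is not prognostic, the gain is nil.

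Two stronger readings should be resisted. The omission does not bias the estimate or inflate type I error; the unadjusted model remains valid. Nor is the remedy entirely free or a mere wording change at any time. With so few responders the adjusted test ran slightly above the unadjusted one under the null. A covariate added after unblinding would also be post hoc: Protocol 6.4 unblinds core team members at the primary-analysis lock, and SAP 2.14 reports the primary endpoint analysis as already performed.

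**What to change.** Before the Week 16 unblinding, add one named covariate to the H11 logistic model in Protocol 12.5.1: the mean of the four main ASAS domains at baseline (patient global, total back pain, BASFI, and the mean of BASDAI items 5 and 6), all on a 0–10 scale. State how a missing domain is handled. Keep disease condition and weight in the model, and keep the marginal difference in proportions as the estimate. Use the single mean rather than four terms, given about 52 expected responders.

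If the Week 16 analysis has already been run, leave the specified H11 test as it is and report the adjusted model only as a labelled sensitivity analysis.

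In the same edit, reconcile the protocol summary, which lists no baseline score for any binary secondary endpoint, with the H2 and H10 models in 12.5.1.

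The cost is one derived variable from data already collected and a few lines of text, with no new assessments or subjects.
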